## Study Protocol

In this study, the combination of Pericapsular Nerve Group (PENG) block and low-dose intrathecal morphine with spinal anesthesia in hip arthroplasty is aimed to be compared with PENG alone and intrathecal morphine alone in terms of morphine consumption, postoperative pain, and recovery quality scores during the postoperative 48-hour period.

After approval from the Ethics Committee of Bezmialem Vakif University Medical Faculty, the study will be conducted on 90 adult patients aged 18-90 years, classified as ASA I-IV, who will undergo hip surgery. This prospective, randomized, and double-blind clinical trial has been planned. Randomization will be achieved by assigning patients to study groups entirely by chance, and selection bias will be prevented. For this purpose, MedCalc version 16 statistical software for Windows ([medcalc.com.tr](http://medcalc.com.tr)) will be used. Patients will be divided into three groups: Pericapsular nerve group block plus spinal anesthesia with bupivacaine (Group P: n=30), Spinal anesthesia with bupivacaine and morphine (Group M: n=30), and pericapsular nerve group block plus spinal anesthesia with bupivacaine and morphine (Group P+M: n=30). After the patients are taken to the operating room, standard monitoring with non-invasive blood pressure (NIBP), heart rate (HR), peripheral oxygen saturation (SpO2), and electrocardiography (EKG) will be conducted. All patients will receive 2-6 L/min of oxygen through a nasal cannula. Preoperative visual analog scale (VAS) for pain and Quality of Recovery (QoR-15) values will be recorded for all patients. As premedication, all patients will receive 0.03 mg/kg midazolam.

In this prospective, double-blind, randomized clinical trial, researchers will be unaware of which treatment will be applied to patients in the study groups and which of these treatments is beneficial or not. Patients will also be unaware of which treatment is administered to them.

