### Groups:

**Group P:** Patients in this group will undergo ultrasound-guided block using a linear or convex ultrasound probe in the supine position before spinal anesthesia. The block procedure will involve the use of a local anesthetic solution (10-20 ml of 0.25% bupivacaine, 2 mg dexamethasone, and 5 mcg.ml-1 epinephrine) and a Stimuplex Ultra 360 22G 80 mm block needle (B. Braun Medical AG, Melsungen, Germany). Subsequently, spinal anesthesia will be administered at the L3-L4 intervertebral level with 10-15 mg of heavy bupivacaine while the patient is in a sitting position.

**Group M:** Patients will receive subarachnoid block without Pericapsular Nerve Group block. Subarachnoid block will be administered at the L3-L4 intervertebral level by adding 10-15 mg bupivacaine with 100 µg of morphine.

**Group P+M:** Patients will undergo ultrasound-guided block using a linear or convex ultrasound probe in the supine position before spinal anesthesia. The block procedure will involve the use of a local anesthetic solution (10-20 ml of 0.25% bupivacaine, 2 mg dexamethasone, and 5 mcg.ml-1 epinephrine)

and a Stimuplex Ultra 360 22G 80 mm block needle (B. Braun Medical AG, Melsungen, Germany). Subarachnoid block will be administered at the L3-L4 intervertebral level by adding 10-15 mg bupivacaine with 100 µg of morphine.

Sensory block control at T8-T10 level will be assessed in all three groups. Visual analog scale (VAS) for pain and 15-degree leg elevation will be measured in all groups 10 minutes after the completion of the block. Postoperative nausea and vomiting will be monitored and recorded. The same anesthesiologist will administer both the block and spinal anesthesia to all patients.

After the block, all patients will be continuously monitored for signs of local anesthetic toxicity every 5 minutes with non-invasive blood pressure, continuous EKG, and pulse oximetry, for 30 minutes. During the perioperative period, VAS (at 1st, 6th, 12th, 24th, and 48th hours), QoR-15 score values, and rescue analgesic requirements of patients will be recorded.

Intravenous Patient-Controlled Analgesia (IV PCA) device will be installed, and patients who are hemodynamically and respiratory stable in the recovery unit will be transferred to the ward.

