### Statistical Analysis

Descriptive statistics for qualitative variables in the study are presented as counts and percentages, while descriptive statistics for quantitative variables include mean, standard deviation, median, minimum, and maximum values. For comparisons based on the occurrence rates of relevant variables among groups, Pearson chi-square or Fisher Freeman Halton tests will be employed. In the detailed comparison of groups with observed differences, the Bonferroni correction will be applied. The normal distribution conformity of quantitative variables will be assessed using the Kolmogorov-Smirnov test. One-way analysis of variance (ANOVA) will be utilized for the comparison of means among more than two groups, with the Tukey test employed as a post hoc test for multiple comparisons. Kruskall-Wallis test will be applied for the median comparison of more than two independent groups, and Dunn test will be used for pairwise comparisons. For repeated measurements of variables showing normal distribution changes between periods, analysis of variance will be applied, while the Friedman test will be used for variables not showing normal distribution. Additionally, two-way analysis of variance will be used to

examine changes between groups and periods. The statistical significance level will be set at 0.05, and the SPSS (version 26) package program will be used for calculations. Consent to conduct the study was obtained from Local Ethic Committee of Bezmialem Vakif University.

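### The named within-patient tests drop any patient who misses one of the five VAS readings, and the plan names no method that both uses incomplete series and respects repeated measurement

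*Combined protocol and SAP*

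**What the plan says.** The Study Protocol section states that "the study will be conducted on 90 adult patients aged 18-90 years", in three arms of 30. VAS is scheduled after surgery as "VAS (at 1st, 6th, 12th, 24th, and 48th hours" in the Groups section. There are two earlier readings. One is before surgery: "Preoperative visual analog scale (VAS) for pain and Quality of Recovery (QoR-15) values will be recorded for all patients". The other "will be measured in all groups 10 minutes after the completion of the block".

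The Statistical Analysis section gives two rules for change over time. "For repeated measurements of variables showing normal distribution changes between periods, analysis of variance will be applied" is the rule for normal variables. For the rest, "while the Friedman test will be used for variables not showing normal distribution". A further sentence begins "Additionally, two-way analysis of variance will be used to" and goes on to cover changes across groups and periods. The same section separately names one-way ANOVA with Tukey, and Kruskal-Wallis with Dunn, for comparing groups.

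The documents do not say how missed readings are handled, which patients form the analysis population, which of these tests applies to VAS, or whether the two-way analysis treats period as a within-patient factor.

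**The concern.** The Friedman test ranks each patient's readings across all periods, and classical repeated-measures ANOVA works on a complete row per patient. With five scheduled readings, one gap discards the other four. This is a property of the methods; the plan does not state it, but has no rule to prevent it.

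Two things are at stake. First, if the two-way analysis is run as a repeated-measures model, the only named test that joins group and period would rest on patients with complete series. If missing a reading is related to recovery, those patients need not represent the randomised arms. Second, for VAS that fails the normality check, the within-patient test named is Friedman, which describes change over time and says nothing about a difference between arms.

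**Working it through.** **Inputs from the documents.** Three arms of 30 give 3 × 30 = 90 patients. There are five postoperative VAS readings, so 90 × 5 = 450 readings. The plan gives no power, effect size, SD or dropout rate with the figure of 90, so there is no calculation of its own to reproduce.

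**Inputs assumed.** Each reading is missed with probability m = 3%, 5% or 10%, independently. The within-patient correlation is 0.5, the same for every pair of readings.

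**Step 1: which tests lose the patient.** In a simulated 90 × 5 data set with one missing cell:
- Friedman can use 89 patients.
- A balanced repeated-measures ANOVA routine rejects the data until that patient is removed.
- A group comparison at each hour uses 89 patients at the affected hour and 90 at the other four.

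**Step 2: complete rows.** The share of patients with all five readings is (1 − m)^5.

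| m | Share complete | Of 30 per arm | Of 90 |
|---|---|---|---|
| 3% | 0.97^5 = 0.859 | 25.8 | 77.3 |
| 5% | 0.95^5 = 0.774 | 23.2 | 69.6 |
| 10% | 0.90^5 = 0.590 | 17.7 | 53.1 |

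At m = 1% or 2%, 85.6 or 81.4 of 90 remain. If the preoperative and 10-minute readings were added to the series (seven readings), the complete share at 5% and 10% would be 0.698 and 0.478.

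**Step 3: clustering.** Independence gives a larger loss than misses that fall in the same patients. With 20 of 450 readings missing, the patients dropped number between 20 ÷ 5 = 4 and 20.

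**Step 4: complete rows against all available readings, for the average level over 48 h.** A patient with k readings carries information k / (1 + (k − 1) × 0.5), so a complete row carries 5/3 = 1.667. Relative information is (1 − m)^5 × 1.667 divided by the expected information over k available readings:
- 3%: 1.431 / 1.656 = 0.864
- 5%: 1.290 / 1.649 = 0.782
- 10%: 0.984 / 1.630 = 0.604

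**Step 5: hour-by-hour tests against a mixed model, at a single hour.** Taking full data as 1, a test at one hour has information 1 − m. The mixed model recovers a little more from the other hours; its information comes from inverting the expected information matrix over all patterns of missing readings:
- 3%: 0.970 / 0.982 = 0.988
- 5%: 0.950 / 0.969 = 0.980
- 10%: 0.900 / 0.936 = 0.961

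Hour-by-hour group tests therefore keep about 99%, 98% or 96% of what the mixed model has at that hour. Steps 4 and 5 count no gain from adjusting for preoperative VAS.

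**The case against.** A reader might infer that one missed VAS removes the patient from the pain analysis altogether. The documents do not support that. The one-way ANOVA and Kruskal-Wallis tests in the same section, applied at each hour, lose the patient only at the missed hour. Against those tests the fix gains about 1-4% in precision, so the losses in Step 4 apply only to tests that need the full row. This part of the objection stands and limits the point.

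A reader might also infer that row loss in Friedman biases the comparison of arms. It cannot, because Friedman compares no arms. A selected comparison could arise only in the two-way analysis, and only if that is run as a repeated-measures model. Run on one row per reading, it would keep incomplete patients but ignore the correlation within a patient.

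It is also fair to say that nothing in the documents shows missed readings to be frequent. No missing rate or discharge time is given, and no primary endpoint is named, so the weight of the pain analysis is not settled.

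The objection does not remove the point. The plan never says that the group tests are to be run hour by hour. If they are, they give five separate comparisons, possibly on different patients each time, and no overall test of group by time. Neither form of the one named test that joins group and period is satisfactory once readings are missing.

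**Conclusion.** The point holds for the repeated-measures pain analysis, not for every pain comparison. Repeated-measures ANOVA and Friedman drop any patient without all five VAS readings, and the two-way analysis does the same if it is run as a repeated-measures model. For non-normal VAS, Friedman shows change over time only.

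The size rests on assumed missing rates. At 3%, 5% or 10% missed independently, about 26, 23 or 18 of 30 per arm have complete rows, and clustering would leave more. The benefit of changing is modest against hour-by-hour tests and larger against a complete-row group-by-period analysis. It is a low-cost improvement that should be made, and does not show that the arms as analysed would be biased.

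**What to change.** For VAS from 1 to 48 h, define the group-by-period analysis as a linear mixed model on all available readings, with group, time, group-by-time and preoperative VAS as fixed terms and an unstructured within-patient covariance. Take the P+M v P and P+M v M contrasts from that model. State that patients with missed readings stay in with the readings they have.

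Keep Friedman and other within-arm tests over time as descriptive. Keep hour-by-hour Kruskal-Wallis as a rank-based sensitivity check if residuals are clearly non-normal.

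The cost is analysis wording only. The preoperative VAS is already collected, the named package has a mixed-model procedure, and no assessment or sample size changes. The model assumes that readings are missing at random, which is weaker than what a complete-row analysis needs, and it relies on approximately normal residuals.

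### The plan does not say whether period is a within-patient factor in the two-way ANOVA of groups and periods; a repeated-measures model should be named

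*Combined protocol and SAP*

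**What the plan says.** The sentence at issue, in the Statistical Analysis section, is split by a page break but complete: "Additionally, two-way analysis of variance will be used to" "examine changes between groups and periods". It names no outcome, no list of periods, no patient term and no sphericity correction.

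The sentence before it deals with repeated readings: "For repeated measurements of variables showing normal distribution changes between periods, analysis of variance will be applied", and otherwise "the Friedman test will be used for variables not showing normal distribution". It does not mention group. Group comparisons are covered separately: "One-way analysis of variance (ANOVA) will be utilized for the comparison of means among more than two groups", and "Kruskall-Wallis test will be applied for the median comparison of more than two independent groups".

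The Groups section schedules "VAS (at 1st, 6th, 12th, 24th, and 48th hours" and adds that "QoR-15 score values, and rescue analgesic requirements of patients will be recorded", without giving QoR-15 times. VAS is also taken before surgery (Study Protocol section) and 10 minutes after the block (Groups section). The aim in the Study Protocol section lists pain after surgery, over 48 hours, as one of three outcomes.

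**The concern.** Five VAS readings from one patient are normally correlated. An ordinary two-way ANOVA treats all readings as independent; a mixed repeated-measures ANOVA does not. The two give very different error rates, and the wording fits either.

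This is the only planned analysis that takes group and period together. The sentence most naturally targets whether the course of pain differs between groups, that is, the group-by-period interaction. On the literal reading that test loses most of its power, while the accompanying overall group test rejects too often.

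**Working it through.** **Inputs from the plan.** 3 groups of 30 patients, 5 VAS times after surgery, significance level 0.05. Readings: 90 × 5 = 450. The plan gives no figure of its own to reproduce beyond the nominal 5%.

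**Assumptions.** The documents give no within-patient correlation, so it is varied. Data are normal and complete, with no true group effect or interaction. Simulations used 20,000 trials per setting.

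**Reading 1: ordinary two-way ANOVA.** Take unit variance and a common correlation ρ between any two readings of a patient.

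- Residual df: 450 − 15 = 435, made up of 87 between patients (3 × 29) and 348 within patients (87 × 4).
- Expected pooled residual mean square: [87(1 + 4ρ) + 348(1 − ρ)] / 435 = 1.
- Expected group mean square: 1 + 4ρ, so the group test is too liberal.
- Expected group-by-period mean square: 1 − ρ, so the interaction test is too conservative.
- Approximate rejection rate of the group test: exp(−F_crit / (1 + 4ρ)), with F_crit(2, 435) = 3.016. At ρ = 0.3 this is exp(−3.016 / 2.2) = 0.254.

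| ρ | Group test, formula | Group test, simulated | Group-by-period, simulated |
|---|---|---|---|
| 0.1 | 11.6% | 11.5% | 2.9% |
| 0.3 | 25.4% | 25.3% | 0.4% |
| 0.5 | 36.6% | 37.1% | 0.01% |
| 0.7 | 45.2% | 45.2% | 0% |

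Cost in power: for an interaction that a repeated-measures ANOVA detects with 80% power, the ordinary ANOVA has about 63% at ρ = 0.2, 51% at 0.3, 19% at 0.5 and 1% at 0.7.

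**Reading 2: mixed repeated-measures ANOVA.** Group is tested on 87 df and group-by-period on 348 df. The group test stays at 4.5 to 5.3% throughout. The uncorrected group-by-period test behaves as follows:

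- Common correlation: 5.0 to 5.2%.
- Equally spaced AR(1) with 0.3, 0.5, 0.7, 0.8: 5.5%, 6.7%, 7.5%, 8.2%.
- Actual hour spacing, correlation halving every 3, 6, 12, 24 or 48 h (true Greenhouse-Geisser epsilon 0.96, 0.86, 0.73, 0.62, 0.55): 5.4%, 6.0%, 7.1%, 8.1%, 9.2%.
- With the Greenhouse-Geisser correction: 4.6 to 5.1%.

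**Group comparison at one time.** One-way ANOVA at 24 h rejects 4.8 to 5.4% in every setting, because each patient contributes one value.

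**Baseline adjustment.** Adjusting for preoperative VAS multiplies residual variance by 1 − r². At an assumed r of 0.2 this is 0.96 and at 0.5 it is 0.75, a reduction of 4 to 25%.

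**Missing readings, illustration only.** If a fraction m of readings is missing independently, a complete-case repeated-measures ANOVA loses 1 − (1 − m)^5 of patients: 4.9%, 9.6% and 22.6% for m = 1%, 2% and 5%. The documents give no missing-data rate, and clustering of missing readings within patients would lower the loss.

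**If QoR-15 is covered with two periods (assumed).** The ordinary group test gives exp(−3.048 / (1 + ρ)) = 6.3%, 9.6%, 13.1% and 16.6% at ρ = 0.1, 0.3, 0.5 and 0.7. Sphericity does not arise with two periods.

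**The case against.** The strongest reply is that the text is silent, not wrong. The preceding sentence concerns repeated measurements, calls a repeated-measures test simply analysis of variance, and pairs it with Friedman, so its authors know that the readings repeat. The sentence at issue follows directly and speaks again of changes and periods. A mixed design is then a natural reading, and on it the group test is sound. This stands, and it is why the 12 to 45% cannot be taken as the plan's actual error rate.

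A reader might also infer that preoperative VAS goes unused. The documents do not support that: with no list of periods, it may be meant as one of them, as may the reading 10 minutes after the block. Five periods is itself an assumption. Nor is omitting baseline adjustment an error in a randomised trial; it costs precision only.

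Finally, the damage is limited. Group tests at single times remain valid, as does a comparison of one morphine total per patient. What the objection does not remove is that the wording permits an invalid analysis, and that no sphericity correction is stated on the favourable reading.

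**Conclusion.** The point holds as an ambiguity with a real downside, and it should be fixed. It would be tempting to conclude that the plan treats 450 readings as independent. The documents do not say so, and their context points at least as much the other way.

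If the sentence is followed literally, the group test rejects about 12 to 45% under no effect at assumed ρ of 0.1 to 0.7, and the group-by-period test 3% or less. The direction holds for any positive common correlation; the size depends on ρ. If a mixed ANOVA is intended, the remaining issue is modest: an uncorrected group-by-period test at about 5 to 9%, depending on how correlation decays, and possibly some lost precision. All figures rest on normal, complete data; non-normal VAS was not simulated.

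**What to change.** Replace the sentence with wording such as:

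> VAS at 1, 6, 12, 24 and 48 h will be analysed with group as between-patient and period as within-patient factor, with preoperative VAS as covariate, by repeated-measures ANOVA with Greenhouse-Geisser correction, or by a linear mixed model with a stated within-patient covariance, which also keeps patients with a missing reading.

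One of the two models should be chosen before the data are seen. Keep the planned Kruskal-Wallis tests at each time for non-normal VAS. State that Friedman has no group factor, so it cannot stand in for the combined analysis. If the sentence also covers QoR-15, say so and list its periods.

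The cost is one or two sentences and slightly more analysis work, with the same data and no change to conduct. If an unstructured mixed model is chosen, its group-by-period F is slightly liberal at this size: 5.5 to 6.1% in a single simulation on complete data that has not been repeated. On complete data, the Greenhouse-Geisser version stays closer to 5%; the mixed model's advantage is with missing readings.

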During the postoperative period, all patients will receive 1 g of intravenous paracetamol every 8 hours. Morphine PCA (concentration: 0.1mg/ml, bolus dose: 1 mg, lockout time: 10 minutes, basal infusion rate: 0 mg) will be adjusted, and intravenous Patient-Controlled Analgesia (PCA) will be applied.

Rescue analgesia will be provided with 50 mg tramadol upon request or when  $VAS \geq 4$  and will be recorded.

Patients experiencing nausea or vomiting at any time will receive ondansetron intravenously at a dose of 0.15 mg/kg, and this dose will be repeated if necessary.

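### No primary outcome or success rule is named, so any one of three equally ranked outcomes can carry the conclusion at 0.05

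*Combined protocol and SAP*

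**What the plan says.** The Study Protocol section sets the aim as a comparison of three outcomes, "in terms of morphine consumption, postoperative pain, and recovery quality scores during the postoperative 48-hour period". None is ranked above the others. The combination is to be "compared with PENG alone and intrathecal morphine alone", with 30 patients in each of three groups. Nothing says whether it must beat both comparators or whether one is enough.

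The Groups section says that "VAS (at 1st, 6th, 12th, 24th, and 48th hours), QoR-15 score values, and rescue analgesic requirements of patients will be recorded". It singles out none of the five VAS hours and gives no postoperative time for QoR-15. Tramadol is a second source of analgesia: "Rescue analgesia will be provided with 50 mg tramadol upon request".

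The Statistical Analysis section chooses tests by type of variable and sets one level: "The statistical significance level will be set at 0.05". Its corrections are:
- for rates: "In the detailed comparison of groups with observed differences, the Bonferroni correction will be applied";
- for means after ANOVA: "with the Tukey test employed as a post hoc test for multiple comparisons";
- after Kruskal-Wallis: "Dunn test will be used for pairwise comparisons", with no adjustment stated.

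A two-way analysis of groups and periods is planned as an addition. It is not named as the deciding test.

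**The concern.** Every correction in the plan deals with pairs of groups inside one variable. None governs the choice among variables. Followed as written, the plan lets morphine use, VAS or QoR-15 each support the statement that the combination is better, and the choice can be made after the data are seen. The two contrasts in the aim appear only as two of three unranked post hoc pairs.

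Two things are at stake. The chance of a false favourable claim is higher than for a single primary outcome. A reader also cannot tell in advance which result would count as success, and that second harm does not depend on any calculation.

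**Working it through.** **Inputs from the documents.** Three groups of 30; three outcomes in the aim; level 0.05; F test followed by Tukey for normal data; five postoperative VAS hours.

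**Assumptions.** The documents give no correlation between outcomes, so a common value from 0 to 0.7 is used. Data are normal and pairwise tests two-sided. There is no stated error rate, power or sample-size calculation to reproduce.

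**1. Any false omnibus result, no true differences.** For three independent outcomes: 1 − 0.95³ = 0.143. Simulation of the F tests gives about 0.14 at correlation 0, falling to about 0.11 at 0.7. This is 11–14%. It counts P vs M differences and results against P+M.

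**2. False favourable claim: Tukey shows P+M better than at least one comparator.** On one outcome, simulation gives about 0.016. A rough check: Tukey spreads 0.05 over three pairs in two directions, and two of those six outcomes favour P+M, so 0.05 × 2/6 ≈ 0.017. For three independent outcomes: 1 − (1 − 0.016)³ = 0.047. Simulation gives about 0.047 at correlation 0 and 0.038 at 0.7, so about 4–5%.

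**3. Reference rates for one primary outcome.** The planned Tukey gives 1.6%. A Dunnett pair for the two contrasts in the aim, counting only favourable results, gives 0.024–0.026, or 2.5%.

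**4. Only if each VAS hour is also tested on its own.** The tests number 5 + 1 + 1 = 7.
- Omnibus, independent: 1 − 0.95⁷ = 0.302; with correlation up to 0.7, 18–30%.
- Favourable claim, independent: 1 − (1 − 0.016)⁷ = 0.107; with correlation, 6–11%.

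The Statistical Analysis section neither states nor excludes these hourly tests.

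**5. P+M must beat both comparators, with one joint VAS test.** A demanding null has P worse by 3 SD and P+M equal to M, so a false claim rests on the single pair P+M vs M. The Tukey critical value for three groups and 87 degrees of freedom is 3.372. Dividing by √2 gives a t value of 2.384, with one-sided probability 0.0096. Over three independent outcomes: 1 − (1 − 0.0096)³ = 0.029. Simulation gives 0.029, 0.027 and 0.023 at correlation 0, 0.5 and 0.7. This is 2–3%, against about 2.5% for one primary outcome with both contrasts at two-sided 0.05.

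**6. Power to beat both comparators, with equal true effects on all three outcomes.**

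| True effect | Plan, success on any of three outcomes (Tukey) | One primary, both contrasts at 0.05 |
|---|---|---|
| 0.8 SD | 82–95% | 78% |
| 0.7 SD | 68–86% | 64% |

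The effect sizes are assumed. Naming one primary outcome lowers power on this comparison.

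These figures describe the ANOVA and Tukey route. None is offered for the rank route, because results simulated on normal data say little about the skewed data for which that route is meant.

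**The case against.** The strongest reply is that the error is modest. A rate of 4–5% sits close to the nominal 0.05, and Tukey already holds a single outcome to 1.6%. That is fair as to size. But the 4–5% counts favourable claims only, so it should be compared with 2.5% or 1.6%, and against the latter it is more than double.

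The aim also gives a 48-hour window. This stands in part: it is a natural period for cumulative morphine, so it would be too strong to say that no time frame exists. The same window covers VAS and QoR-15 without choosing a time for either.

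A reader might infer that the combination has an 11–14%, or even 18–30%, chance of a false success. The documents do not support that. The first range includes results that have nothing to do with P+M being better. The second also needs separate tests at each VAS hour, which the plan does not state, and the planned group-and-period analysis could serve as one joint test.

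A reader might also infer that naming a primary outcome and planned contrasts would gain power. It would do so only against a plan judged on one outcome. Against a rule that accepts any of three, with effects on all three, power falls.

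Finally, no sample-size rationale appears in the sections reviewed, so nothing shows that 30 per group suits whichever primary outcome and win rule are chosen. That objection stands as a limit on the fix.

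**Conclusion.** The point holds for the Study Protocol, Groups and Statistical Analysis sections. The opening pages were not in the text reviewed. The gap is the missing choice among outcomes and the missing win rule. It is not an absence of multiplicity control, because comparisons between groups within a variable are largely covered, apart from the unstated adjustment for Dunn.

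If beating either comparator counts as success, the false favourable rate is about 4–5% in place of 1.6–2.5%. If both must be beaten, there is no inflation with one joint VAS test. These sizes rest on normal data, a global null (for the both-comparators case, the null in step 5) and an assumed correlation of 0 to 0.7. The lack of a conclusion fixed in advance rests on none of them. The trial can run unchanged, but this should be settled before unblinding.

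**What to change.** Before unblinding, add to the Statistical Analysis section:

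1. One primary outcome, for example cumulative 48-hour morphine consumption. State whether recorded tramadol is included, with the conversion fixed in advance, or reported alongside.
2. P+M vs P and P+M vs M as the confirmatory contrasts, and whether both or either must succeed.
3. One alpha rule. If both must succeed, test each at two-sided 0.05. If either is enough, use Dunnett, or Holm-adjusted Wilcoxon tests if the data are not normal.
4. QoR-15, VAS (including single hours), P vs M and all other outcomes as secondary and descriptive.

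This needs analysis wording only, with no extra patients or measurements. The cost is that secondary outcomes carry no confirmatory claim. The sponsor should also expect that, if both comparators must be beaten, 30 per group gives about 64% power at an assumed 0.7 SD and 78% at 0.8 SD.
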